## **4.3 Subject Registration**

### **4.3.1 Subject Registration**

Based on medical history, potentially eligible subjects will be identified. After obtaining informed consent, the screening procedures will be performed. Once a subject's eligibility has been confirmed, a 4-digit subject number will be assigned. The first 2 digits are the site number (provided by the Sponsor or CRO to investigational sites). The following 2 digits are a sequential number within an investigational site. An Eligibility Screening Form (ESF) provided by the Sponsor or CRO documenting the Investigator's assessment of each screened subject with regard to the protocol's inclusion and exclusion criteria is to be completed, submitted for review and approval by the Sponsor or Sponsor representative and kept at the investigational site

### **4.3.2 Blinding**

This is an open-label study; no blinding procedures will be performed.

## **4.4 Withdrawal Criteria**

### **4.4.1 Subject Withdrawal from the Study**

Subjects may withdraw from the study at any time for any reason. The Investigator should try to ascertain the reason for withdrawal as completely as possible. The Investigator may also decide to discontinue a subject from the study. HBI-8000 may be discontinued, and the subject withdrawn from the study under the following circumstances:

- Unacceptable toxicity (AE)
- Progression of the disease under study
- Decision by the Investigator or subject to permanently discontinue HBI-8000
- Intercurrent illness that would, in the judgment of the Investigator, affect clinical assessments, patient safety, or follow-up to a significant degree
- Significant protocol deviations that jeopardize the usefulness of the data

- Subject noncompliance, examples include omitting >1/3 of protocol specified dose over 6 consecutive weeks, not adhering scheduled safety assessments, etc.
- Subject is beginning another anti-cancer treatment
- Subject becomes pregnant
- Subject request to withdraw informed consent
- Death

All subjects who withdraw from HBI-8000 must complete an EoT safety follow-up visit, to be performed 30 ( $\pm$  3) days after the last dose of HBI-8000, or before initiation of new cancer treatment, whichever is earlier. After HBI-8000 is discontinued, the subjects should be followed for disease progression (if not already recorded) and survival. Only subjects who have withdrawn from study participation entirely, including the period after HBI-8000 is discontinued, will not be followed. In other words, a subject may withdraw consent for treatment but still allow follow-up, in which case he/she should be followed for safety, survival, and disease status.

#### **4.4.2 Lost to Follow-up**

All reasonable efforts must be made to locate subjects to determine and report their ongoing status. Lost to follow-up is defined by the inability to reach the subject after a minimum of three documented phone calls, faxes, or emails as well as lack of response by subject to one registered mail letter. All attempts should be documented in the subject's medical records. If it is determined that the subject has died, the site will use permissible local methods to obtain the date and cause of death.

### **4.5 Discontinuation of Investigational Product and Participant Withdrawal**

Subjects discontinued from HBI-8000 for toxicity in the absence of disease progression may continue to receive pembrolizumab under standard of care and be followed for disease response as long as consent to study participation remains effective. Similarly, if pembrolizumab administration is discontinued due to unacceptable toxicities (other than immune-mediated reactions) associated with pembrolizumab, the subject may continue to receive HBI-8000, at the Investigator's discretion in consultation with Sponsor Medical Monitor and be followed for disease response as long as consent to study participation remains effective. When both HBI-8000 and pembrolizumab have been discontinued and disease has not progressed, the subject will continue to be followed for disease status in the Follow-up Phase until evidence of progression.

## 5 STUDY TREATMENT

### 5.1 Investigational Product(s) Administered

Table 3: Investigational Products

Investigational Product	Dosage Form and Strength	
HBI-8000	Immediate-release, 10 mg film coated tablet	
KEYTRUDA®(pembrolizumab)	100 mg/4 mL (25 mg/mL) single-dose vial	

#### 5.1.1 HBI-8000 Information

The HBI-8000 Drug Product is formulated as a coated tablet containing 10 mg of HBI-8000, [REDACTED]

The drug substance, drug product intermediate (dispersion), and film coated tablets are manufactured in the US.

#### 5.1.2 Pembrolizumab Information

Pembrolizumab is a humanized monoclonal IgG4 kappa antibody supplied as a sterile, preservative-free, clear to slightly opalescent, colorless to slightly yellow solution in a single-dose vial for intravenous use.

The vial should be visually inspected for particulate matter and discoloration prior to administration. The solution is clear to slightly opalescent, colorless to slightly yellow. Discard the vial if visible particles are observed.

## 5.2 Clinical Supplies Storage and Accountability

### 5.2.1 Clinical Materials

HBI-8000 Investigational Product tablets are supplied as film coated tablets in a high-density polyethylene (HDPE) bottle containing 26 tablets, a 1-gram silica gel desiccant cannister and a polyester coil for moisture protection. Bottles will be labeled in accordance with GCP, US FDA requirements under Code of Federal Regulations (CFR) 21.201.

### **5.2.2      Investigational Product Storage**

**HBI-8000 Investigational Product:** The storage and distribution condition is 15° to 30° Celsius (59°F to 86° Fahrenheit).

HBI-8000 must be stored out of the reach of children and in original container with tightly closed cap to protect from moisture.

**Pembrolizumab:** Must be stored under refrigeration at 2 to 8°Celsius (36 to 46°Fahrenheit), protected from light by storing it in the original package until time of use. It must not be frozen or shaken.

Pembrolizumab does not contain a preservative. Diluted pembrolizumab from the 100 mg/4 mL vial should be stored either:

- At room temperature for no more than 6 hours from the time of dilution. This includes room temperature storage of the diluted solution, and the duration of infusion.
- Or, under refrigeration at 2°C to 8°C (36°F to 46°F) for no more than 96 hours from the time of dilution. If refrigerated, allow the diluted solution to come to room temperature prior to administration. Do not shake.

Discard diluted pembrolizumab after 6 hours at room temperature or after 96 hours under refrigeration.

Do not freeze.

### **5.2.3      Investigational Product Accountability**

The Investigator, or his/her designee, must maintain a complete and accurate record of the receipt and distribution of all study medication using the Drug Accountability Form provided by the CRO, or local site equivalent.

All study medication must be accounted for at the termination of the study, and a written explanation provided for any discrepancies. The study monitor will conduct a final drug reconciliation for all subjects. All records of HBI-8000 administration, accountability records, and disposition records will be examined and reconciled by the study monitor. All unused, partially used, and expired study medication and packaging materials are to be inventoried and returned to depot or destroyed as per the sites' Standard Operating Procedure (SOP). The timing of the returns will be coordinated with the study monitor. The Investigator is not permitted to destroy unused clinical drug supplies or packaging materials unless authorized by HUYABIO or Sponsor representative.

## **5.3      Investigational Product Compliance**

The prescribed dosage, timing, and mode of administration may not be changed. Any departures from the intended regimen must be recorded in the eCRFs. Treatment compliance will be monitored by drug accountability as well as the subject's medical record and eCRF.

Study subjects will be provided with a drug diary to record times of administration, AEs, and missed doses. Study subjects will be instructed to bring the drug diary and study drug bottles (including empty bottles) to each study visit for reconciliation.

At each visit, prior to dispensing HBI-8000, previously dispensed HBI-8000 will be reviewed by the Investigator or designee and compliance assessed. Subjects exhibiting poor compliance as assessed by tablet counts should be counseled on the importance of good compliance to the study dosing regimen.

## **5.4 Concomitant Therapy**

All concomitant medications, defined as medications other than study medications, which are taken at baseline and throughout HBI-8000 treatment phase by the study subjects must be recorded on the eCRF.

Palliative radiation therapy (limited-field) is permitted only for pain control to sites of bone disease present at baseline. The Sponsor Medical Monitor must be consulted prior to initiating any radiotherapy.

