### **5.4.1 Prohibited Medications and Therapy**

Concomitant administration of the following types of drugs and procedures is not allowed:

- Recently completed drug-drug interaction study showed a mild (approximately 40%) increase of AUC of HBI-8000 when itraconazole, a strong CYP3A4, was administered concurrently. The use of potent CYP3A4 inducers or inhibitors ([Appendix 3](#)) should be avoided.
- Live vaccines within 30 days prior to the first dose of trial treatment and while participating in the trial. Examples of live vaccines include, but are not limited to, the following: measles, mumps, rubella, chicken pox, yellow fever, seasonal flu (that contain a live virus), H1N1 flu, rabies, BCG, and typhoid vaccine.
- Surgery for tumor control or symptoms management is not permitted during the study.
- Concomitant administration of anti-tumor treatment other than the Study Treatment, or procedures that could interfere with the evaluation of safety or anti-tumor effect of Study Treatment, is prohibited during the study.

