### **5.4.2 Supportive Care and Other Medications**

Systemic use of corticosteroids at doses  $\leq$ 10 mg/day of prednisolone, or converted equivalent dose, is permitted during the study. Brief use of higher dose of prednisone or its equivalent is also permitted to manage immune related toxicities as indicated. Supportive care to mitigate toxicities such as anti-emetics for nausea, and granulocyte-colony stimulating factor (G-CSF) for neutropenia are also allowed.

Palliative and supportive care is permitted during the course of the trial for underlying medical conditions and management of symptoms.

Palliative radiation therapy (limited field) is permitted only for pain control if considered medically necessary by the treating physician as long as the lesion is NOT a RECIST 1.1 defined target lesion and is NOT administered for tumor control. Study treatment should be held during the course of palliative radiotherapy and should be resumed no earlier than the next scheduled administration of study treatment. The specifics of the radiation treatment, including the location,

will be recorded. The Sponsor Medical Monitor must be consulted prior to initiating any radiation therapy.

In order to provide optimal patient care, and to account for individual medical conditions, the Investigator may apply discretion to prescribe supportive care (e.g., acetaminophen, diphenhydramine, antimicrobials) according to local institutional guidelines. After the first cycle, pre-medication for anticipated adverse events may also be provided, according to local institutional guidelines.

Subjects must be instructed to first consult with their study doctor before taking any additional medications (including over-the-counter or prescription medications and supplements including those prescribed/recommended by other physicians/dentists) during the study.

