#### **6.2.1.1 Tumor Response Criteria**

All measurable disease (target lesions and non-target lesions) must be documented at screening and reassessed at each subsequent tumor evaluation. Reassessment will be done by imaging studies according to RECIST Guidelines version 1.1 ([Appendix 4](#)), along with physical examinations and other methods as needed. At the Investigator's discretion, CT scans may be repeated at any time if PD is suspected.

Tumor response will be evaluated by the Investigator using the RECIST 1.1 criteria [[Eisenhauer 2009](#)] ([Appendix 4](#)) and recorded in the appropriate eCRFs. Tumor response will also be assessed centrally.

Taking into consideration possible pseudo progression, the subject may continue study treatment until the next imaging evaluation to assess tumor response according to irRECIST criteria. The same scanning modality should be used at baseline and throughout treatment for each subject.

Subjects with isolated CNS progression, but responsive/stable extracranial disease, may remain on the study protocol after consultation with Sponsor Medical Monitor.

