### 7.1 Sample Size Determination

Approximately 20 to 24 subjects are planned to be enrolled to characterize safety and allow for preliminary evaluation of efficacy endpoints in the specific patient population of interest. With a sample size of 20 to 24 subjects the probability that an adverse event with at least a 10% incidence will be detected in at least one subject is high (87.8% to 92.0%) (Table 4). Obtaining this information will help in planning for future immuno-oncology studies.

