### 7.5 Statistical Analyses

#### 7.5.1 Efficacy Analyses

Efficacy analyses will be performed on FAS and PPS. ORR will be estimated based on the proportion of subjects whose best overall response is CR or PR. Disease response will be assessed using RECIST v1.1 as the primary methodology and iRECIST will be used to exclude pseudo-progression when suspected. The estimate of the ORR will be accompanied by a 2-sided

95% exact binomial confidence interval (CI). DCR (CR+PR+SD) will be analyzed similarly. DOR and PFS will be summarized descriptively using Kaplan-Meier methods. The final SAP will provide more details on these analyses.

The efficacy endpoints are the following:

- **Objective Response Rate (ORR)**, defined as the percent of subjects with CR or PR according to RECIST 1.1 and irRECIST criteria, relative to the efficacy population. Subjects who do not have an on-study assessment due to safety issues will be included as non-responders.
- **Disease Control Rate (DCR)**, defined as the percent of subjects with CR, PR or SD according to RECIST 1.1 and iRECIST criteria, relative to the efficacy population.
- **Duration of Response (DoR)**, defined as the time from documentation of tumor response to disease progression.
- **Progression-Free Survival (PFS)**, defined as the time from the start of treatment (Day 1 Cycle 1) until objective tumor progression or death.

The EoT Safety Follow-up visit is scheduled  $30 \pm 3$  days after the last dosing of the HBI-8000 or before the initiation of new cancer treatment, whichever is earlier.

Response rate endpoints (ORR, DCR) will be summarized by number and percentage of subjects meeting the definition of ORR and DCR along with the corresponding exact 95% CI based on binomial distribution.

Time-to-event endpoints (DoR, and PFS) will be summarized by Kaplan-Meier methods (median, 95% CI, number of events, number censored, and Kaplan-Meier figures).

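### Sections 5.4 and 5.4.2 give incompatible rules for palliative radiotherapy sites, and no rule says how an irradiated lesion is scored for response.

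*Combined protocol and SAP*

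**What the plan says.** Section 5.4 (Concomitant Therapy): "Palliative radiation therapy (limited-field) is permitted only for pain control to sites of bone disease present at baseline". Target lesions are not mentioned.

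Section 5.4.2 (Supportive Care and Other Medications) also permits limited-field radiotherapy only for pain, but on another condition: "as long as the lesion is NOT a RECIST 1.1 defined target lesion and is NOT administered for tumor control". It does not limit treatment to bone or to disease present at baseline.

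Three other provisions bear on the point:

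- Section 5.4.1 contains a general bar: other anti-tumor treatment, or "procedures that could interfere with the evaluation of safety or anti-tumor effect of Study Treatment, is prohibited during the study". Radiotherapy is not named there.
- Section 5.4 adds: "The Sponsor Medical Monitor must be consulted prior to initiating any radiotherapy". Section 5.4.2 repeats this requirement.
- Section 5.4.2 requires a record of the treatment: "The specifics of the radiation treatment, including the location".

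On assessment, section 6.2.1.1 says: "All measurable disease (target lesions and non-target lesions) must be documented at screening and reassessed at each subsequent tumor evaluation". Response is assessed by the investigator and also centrally. On analysis, section 7.5.1 says: "ORR will be estimated based on the proportion of subjects whose best overall response is CR or PR". Neither section, nor Appendix 4, says how a lesion irradiated during the study is scored.

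**The concern.** There are two separate problems. First, sites reading different sections would apply different rules about which lesions may be irradiated, and one of those rules leaves target lesions open. Second, whichever rule applies, radiotherapy changes lesions that feed the response assessment, and the plan does not say what follows from that.

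Both effects tend to favour the treatment. Section 3.1 describes an open-label, non-randomized study, so there is no concurrent control group in which the effect would cancel. Section 7 requires the detailed SAP to be final only before database lock, so a handling rule left to that document could be chosen when responses are already known.

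**Working it through.** **Plan's own figure.** The only design figure is the chance of seeing at least one adverse event of 10% incidence (section 7.1, Table 4). It is 1 − (1 − 0.10)^n, giving 87.84% for n=20 and 92.02% for n=24, which matches the stated 87.8% and 92.0%. This point does not depend on it.

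**Step 1: the two rules side by side**, all for pain control:

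| Lesion | 5.4 alone | 5.4.2 alone | Both applied |
|---|---|---|---|
| Bone, at baseline, target | permitted | barred | barred |
| Bone, at baseline, non-target | permitted | permitted | permitted |
| Bone, new since baseline | barred | permitted | barred |
| Outside bone, non-target | barred | permitted | barred |
| Outside bone, target | barred | barred | barred |

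The sections disagree in three of five rows, in both directions. The first row can arise because Appendix 4 as reproduced does not exclude bone lesions from target selection.

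**Step 2: what an irradiated lesion can change**, using the criteria and overall-response table in Appendix 4:

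- *Target lesion.* PR needs a fall of at least 30% in the sum of target diameters. Shrinkage from radiotherapy lowers that sum and can contribute to a PR, and so to ORR.
- *Non-target lesion, PR to CR.* Target CR with persisting non-target disease is PR; target CR with non-target CR is CR. Radiotherapy can move a subject from the first to the second. Both count in ORR.
- *Non-target lesion, averted progression.* Non-target PD alone makes the overall response PD. If radiotherapy prevents it, the subject keeps SD or PR, which favours DCR, PFS and DoR.

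The last two effects arise even when both sections are applied together, because non-target bone sites present at baseline remain permitted.

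**Step 3: scale.** The planned sample size comes from section 7.1: "Approximately 20 to 24 subjects are planned to be enrolled to characterize safety and allow for preliminary evaluation of efficacy endpoints". If every subject is in the analysis set, one subject is 1/24 = 4.2 points or 1/20 = 5.0 points of a response proportion.

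As an illustration with assumed counts at n=24, 8 responders give 33.3% (exact 95% CI 15.6 to 55.3) and 9 give 37.5% (18.8 to 59.4). A one-subject shift is small against an interval about 40 points wide (55.3 − 15.6 = 39.7).

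**The case against.** The strongest reply is that both sentences are restrictions, so a site must satisfy both. Together they give a workable rule: pain control only, bone disease present at baseline, not a target lesion. The general bar in 5.4.1 and the Medical Monitor consultation point the same way, and central assessment adds a check.

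Much of this stands. Section 5.4.2 bars target lesions expressly, so the target-lesion route to ORR needs a site to follow 5.4 alone. But nothing says that the two conditions are cumulative, and 5.4.2 taken by itself permits lesions that 5.4 forbids. Consultation supplies no criterion for choosing between them, and central assessment comes with no rule for irradiated lesions. Sections 7 and 7.5.1 leave detail to the final SAP, which could hold such a rule; the text available does not.

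A reader might infer three stronger things that the documents do not support:

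- *That irradiating non-target lesions inflates ORR.* Under RECIST 1.1 in Appendix 4, non-target shrinkage cannot create a PR. One narrow exception remains: target lesions already meet PR or CR, and radiotherapy averts non-target PD before the response is recorded.
- *That irradiating a new lesion hides progression.* Under RECIST 1.1, which section 7.5.1 makes the primary method, a documented new lesion is always PD, and later radiotherapy does not undo it. Sections 6.1.3 and 6.2.1.1 also provide for earlier imaging when progression is suspected. The immune-related criteria do add new lesions to the sum, but section 7.5.1 gives them the role of excluding suspected pseudo-progression, although its ORR definition names them too.
- *That the bias has a known ceiling.* No radiotherapy rate is given, so nothing bounds the number of affected subjects.

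**Conclusion.** The contradiction is wrong as written and needs reconciling. The missing scoring rule is a real gap under either section.

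The effect on the primary ORR is conditional: apart from the narrow exception above, it requires a site to act on 5.4 without 5.4.2. The effect on DCR, PFS and DoR through averted non-target progression, and on the split between CR and PR, does not depend on which section is followed.

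The likely size cannot be computed. The 4.2 to 5.0 points per subject is a unit of scale, not an estimate, and assumes an analysis set of 24 to 20; a smaller set would make each subject weigh more. No sample-size or error-rate figure in the plan changes.

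**What to change.** 1. Reconcile sections 5.4 and 5.4.2 into one statement of when radiotherapy is permitted. Which sites to permit is the sponsor's clinical decision and is not judged here.
2. State in sections 6.2.1.1 and 7.5.1 that a lesion irradiated on study is scored not evaluable from that date. It then cannot support a CR, or a PR if it is a target lesion. Appendix 4 already has the rows needed: target CR with unevaluated non-target disease is PR, and incompletely evaluated target lesions without non-target PD give NE. Progression elsewhere still counts as PD.
3. Pre-specify a sensitivity analysis of PFS and DoR for subjects irradiated before documented PD, for example counting the start of radiotherapy as progression. This is needed because Appendix 4 keeps SD and PR when non-target lesions are not all evaluated, so item 2 does not address averted progression. Reporting how many such subjects count toward DCR would cover that endpoint.

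The cost is protocol wording, one derivation rule and one sensitivity analysis. Radiotherapy location is already recorded, and the sample size does not change. The downside is that response figures may become slightly less favourable.
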